**SUMMARY**

The SYNT001-103 protocol has been amended under version 2.0 as follows:

- Lengthened subject follow-up to include study visits at Day 84 and Day 112 to follow pharmacodynamics (Serum IgG) and clinical effects out to 12 weeks from the last dose of SYNT001
- Added immune phenotyping to Day 56 assessments
- Contraception requirement in Inclusion and Exclusion criteria updated to correspond to additional study visits (out to Study Day 112; 12 weeks following last dose of SYNT001) for both females and males
- Total blood draw for subjects completing the study at Day 112 updated to approximately 381 mL from 311 mL in Section 6.7
- Allowing vaccinations at the discretion of the Investigator after Day 56
- AE reporting timelines updated to correspond to additional study visits
- Clarifying language for Tetanus and Varicella-Zoster Virus antibody testing follow-up, specifying the actual study visit Days when additional testing will be performed
- Clarifying language for Investigator removal of subjects from study to not require consultation with Medical Monitor but to allow it if desired
- Clarifying language for dose escalation stopping rules; rules for stopping escalation are not changed
- Additional text related to potential immune effects and corresponding references added
- Various typographical and formatting corrections as well as corrections for consistency made throughout the document.

---

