# SYNTIMMUNE

11-Aug-2017

**Protocol Number:** SYNT001-103

**Protocol Name:** A Phase 1b, Multicenter, Open-Label, Safety, Tolerability, and Activity Study of SYNT001 in Subjects with Chronic Pemphigus (Vulgaris or Foliaceus)

**IND Number:** 132727

**Study Drug:** SYNT001

**Protocol Version, Date:** 2.0, 12-April-2017

**Clarification Letter Version:** 2.0

**Subjects:** Infusion Reactions  
Concomitant Medications and Treatments  
Adverse Event Reporting

The purpose of this memo is to present planned revisions and required corrections in the protocol text resulting from requests for clarification from Investigators. Text regarding management of infusion reactions has been revised. Text regarding pre-medications has been added and text regarding adverse events that require reporting within 24 hours has been corrected. Deleted text is crossed through and new text is in italics.

This text will be formally revised in the next forthcoming protocol amendment. In the interim please provide this correspondence to your Institutional Review Board as per local policy.

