## Section 10 (page 69)

Current text: All treatments a subject receives within 14 days prior to enrollment through the end of the study will be documented. Concomitant medication and treatment for co-existing conditions, including those for pemphigus, are permitted if not excluded below. Topical antibiotics are permitted to treat active infections that occur on study. Topical or systemic treatments for oral candidiasis are permitted. Topical lidocaine for transient pain relief is acceptable as needed. Significant increases in anti-pemphigus medications will result in subjects being discontinued from the study. Concomitant treatment that is medically indicated for any AEs the subject experiences during the study are permitted.

Revised text: All treatments a subject receives within 14 days prior to enrollment through the end of the study will be documented. Concomitant medications and treatments for co-existing conditions, including those for pemphigus, are permitted if not excluded below. Topical antibiotics are permitted to treat active infections that occur on study. Topical or systemic treatments for oral candidiasis are permitted. Topical lidocaine for transient pain relief is acceptable as needed. Significant increases in anti-pemphigus medications will result in subjects being discontinued from the study (*See Section 8.4.3*). Concomitant treatment that is medically indicated for any AEs the subject experiences during the study are permitted. *Premedication is discouraged as prophylaxis against AEs or infusion reactions unless medically indicated from either past medical history, prior infusion reactions or AEs resulting from SYNT001 infusions.*

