	related SAE or any study drug-related non-SAE adverse event that, in the judgement of the Investigator (following consultation with the Medical Monitor, if desired) suggest that it could be unsafe to administer further study drug to that subject. Additionally, a subject will be discontinued from further treatment with study drug, at the discretion of the Investigator with consultation with the Medical Monitor, if they require a significant increase in dose(s) of anti-pemphigus medication(s) for the management of pemphigus.
Pharmacokinetics	
The PK of SYNT001 will be evaluated following the first and last (fifth) doses of SYNT001.
 
Starting on Days 0 and 28, serum samples will be collected just prior to the start of study drug infusion (pre-dose), at 5 minutes and 2, 4, 6, 24, and 48 hours after the end-of-study drug infusion. Additional samples will be collected on Days 5 and 33.
 
Study drug concentration will be used to calculate the following PK parameters: <math>t_{1/2}</math>, <math>C_{max}</math>, <math>T_{max}</math>, <math>AUC_{0-24}</math>, and <math>AUC_{0-\infty}</math>.

Pharmacodynamics/ Activity	PD samples will be collected for analysis of IgG (serial assessment of IgG levels to identify $C_{min}$ , $T_{min}$ ); IgG1-4 subtype levels; IgA levels; IgM levels; albumin levels; anti-Dsg (1 and 3) antibody levels; serum AECA by direct immunofluorescence; CIC; C3; exploratory biomarkers ( FCGR2A SNP, RNAseq, urine IgG, $CD3^+CD4^+$ T, $CD3^+CD8^+$ T, monocytes, NK cells and B cells), and additional exploratory analyses to investigate immune response associated with pemphigus.
Immunogenicity	Samples will be collected for immunogenicity analyses on Days 0 (pre-dose), 14, 28, 56, 84 and 112.
Skin biopsy	Optional skin biopsy samples from lesional or non-lesional skin will be collected on Day 0 pre-dose and on Days 1, 2, 14, 33, 56 and 84 to analyze SYNT001 levels.
Photography	Photographs of active lesions will be taken at Day 0. Follow-up photographs of the same areas will be taken on Days 33, 56, 84 and 112. Subjects who begin a steroid taper will have additional photographs taken at the clinic visit during which the decision to begin the taper is made.

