## 5 STUDY POPULATION

### 5.1 Target Population

This study will be conducted in approximately 16 male and female subjects (2 cohorts of 8 subjects each) with a confirmed diagnosis of pemphigus (vulgaris or foliaceus); however, a third cohort of up to 8 subjects may be added. Subjects will be enrolled only once in the study and will not be included in subsequent dosing cohorts. Subjects who withdraw for any reason other than an AE and who do not receive study drug or have only received one dose of study drug may be replaced, up to one subject per cohort. Subjects who do not receive all doses of study drug will continue to be followed through all scheduled visits. The maximum number of subjects who may be enrolled in this study is 27 (24 + up to 3 replacements, as necessary). Within each dosing cohort, no more than 3 subjects may be enrolled with pemphigus foliaceus.

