## **8.3 Replacements**

Enrolled subjects withdrawn for a reason other than an AE will be replaced if they have not been dosed or have only received one dose of study drug at the time of discontinuation, up to one subject per cohort. Subjects who do not receive all doses of study drug will continue to be followed through all scheduled study visits.

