#### **8.4.3 Individual Stopping Rule**

Dosing for any individual subject will be discontinued (i.e., no further study drug will be given to that subject) if the subject experiences any study drug-related SAE or any study drug-related non-SAE adverse event that, in the judgement of the Investigator (following consultation with the Medical Monitor, if desired) suggest that it could be unsafe to administer further study drug to that subject. Additionally, a subject will be discontinued from further treatment with study drug, at the discretion of the Investigator with consultation with the Medical Monitor, if they require a significant increase in dose(s) of anti-pemphigus medication(s) for the management of pemphigus.

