## 10 CONCOMITANT MEDICATION AND TREATMENT

All treatments a subject receives within 14 days prior to enrollment through the end of the study will be documented. Concomitant medication and treatment for co-existing conditions, including those for pemphigus, are permitted if not excluded below. Topical antibiotics are permitted to treat active infections that occur on study. Topical or systemic treatments for oral candidiasis are permitted. Topical lidocaine for transient pain relief is acceptable as needed. Significant increases in anti-pemphigus medications will result in subjects being discontinued from the study. Concomitant treatment that is medically indicated for any AEs the subject experiences during the study are permitted. Premedication is discouraged as prophylaxis against AEs or infusion reactions unless medically indicated from either past medical history, prior infusion reactions or AEs resulting from SYNT001 infusions.

Use of the following treatments will not be permitted during the study unless otherwise specified:

- Rituximab or other anti-CD20 antibody
- Monoclonal antibodies other than study drug
- Any immunosuppressive drugs apart from corticosteroids, azathioprine, mycophenolate mofetil, or cyclosporine.
- Topical steroids
- Any dietary herbal supplements
- Any investigational drug or device
- Any vaccinations through Day 56. Following Day 56, subjects may be vaccinated at the discretion of the Investigator.

If over a period of at least two weeks on study drug, a subject on corticosteroids shows the absence of new lesions and significant healing of lesions that existed at study baseline, a slow corticosteroid taper may be started as per the following suggested schedule

- If on > 30 mg of prednisone per day, decrease by 10 mg every two weeks until a dose of 30 mg per day then decrease by 5 mg every two weeks
- If on < 30 mg of prednisone per day, decrease by 5 mg every two weeks

In cases in which concomitant medications are used, details to be recorded include the following: medication name, start date and time, stop date and time, dose, route, frequency, and reason for use. The concomitant medication names are to be coded using the World Health Organization (WHO) Drug Dictionary (WHO-DD March 2013, Type B2 or later) and classified by anatomical therapeutic chemical (ATC) categories.

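### A significant increase in pemphigus medication during dosing ends study participation under Section 10, but only study drug, with visits to Day 112, under Sections 8.4.3, 8.3 and 5.1

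*Protocol*

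**What the plan says.** The latest protocol version in the file gives two rules for one event.

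- **Leave the study.** Section 10, and identically the synopsis row on prohibited concomitant treatments: "Significant increases in anti-pemphigus medications will result in subjects being discontinued from the study". No discretion is mentioned.
- **Stop the drug.** Section 8.4.3: "a subject will be discontinued from further treatment with study drug, at the discretion of the Investigator with consultation with the Medical Monitor", the condition being, as the synopsis stopping rule also words it, "if they require a significant increase in dose(s) of anti-pemphigus medication(s) for the management of pemphigus".

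Section 8.3 sets out what follows missed doses: "Subjects who do not receive all doses of study drug will continue to be followed through all scheduled study visits". Section 5.1 says the same: "Subjects who do not receive all doses of study drug will continue to be followed through all scheduled visits". The last scheduled visit is Day 112.

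Section 8 treats leaving the study as a different event. It triggers a best-effort Early Termination visit, which shares the Day 112 column of Table 1.

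Clarification letter 2.0 of August 2017 added a pointer to Section 8.4.3 to the Section 10 sentence and announced: "This text will be formally revised in the next forthcoming protocol amendment". The later version took up that letter's premedication text in the same paragraph but not the pointer.

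**The concern.** A site reading Section 10 takes the subject out of the study. A site reading Section 8.4.3 with 8.3 stops the infusions and keeps every visit. The synopsis contains both rules, so it does not settle the matter. With cohorts of 8 spread over about 10 sites, two subjects with the same event could be handled differently.

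The data at stake bear on safety, the primary objective. The subject has just had pemphigus medication increased, possibly an immunosuppressant, while IgG may be depressed; Section 9.6.2 anticipates a 70% to 80% reduction after multiple doses. Leaving the study ends the serial IgG measurements, the tetanus and varicella-zoster retest sequence, the Day 112 IgG referral check, the recording of unrelated adverse events, later PDAI and anti-desmoglein values, and the record of steroid use after the increase. The version 2.0 summary of changes says that amendment added "study visits at Day 84 and Day 112 to follow pharmacodynamics (Serum IgG) and clinical effects out to 12 weeks from the last dose".

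No direction or size of bias in PDAI is claimed, because values after the increase may also be altered by the added medication.

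**Working it through.** **Do the rules collide?**

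1. *Trigger.* Both rules concern a significant increase in anti-pemphigus medication.
2. *Consequence.* Section 10 ends participation. Section 8.4.3 explains its own term as no further study drug being given, and Section 8 attaches the Early Termination visit to leaving the study. The protocol therefore treats these as distinct events.
3. *Force.* Section 10 is unconditional; Section 8.4.3 leaves the decision to the Investigator after consulting the Medical Monitor.
4. *Period.* The collision runs from the first dose to the Day 28 dose. For a subject who has had all five doses, no drug is left to stop and Sections 8.3 and 5.1 do not apply. Section 10 then acts alone and still ends follow-up.

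**What is lost per affected subject?**

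Post-baseline days, from Table 1:

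- PDAI: 7, 14, 21, 28, 33, 42, 56, 84, 112 (9 time points)
- Anti-desmoglein: 7, 14, 33, 56, 84, 112 (6 time points)
- Immunoglobulins: 1, 2, 5, 7, 12, 14, 19, 21, 28, 29, 30, 33, 42, 56, 84, 112 (16 time points)

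The table counts the days later than the increase. Remaining follow-up is 112 minus the day of the increase. Under Section 10, each row is replaced by one Early Termination set.

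| Increase just after | PDAI | Anti-desmoglein | Immunoglobulins | Days to Day 112 |
|---|---|---|---|---|
| Day 7 | 8 | 5 | 12 | 112 − 7 = 105 |
| Day 14 | 7 | 4 | 10 | 112 − 14 = 98 |
| Day 21 | 6 | 4 | 8 | 112 − 21 = 91 |
| Day 33 (dosing complete, Section 10 alone) | 4 | 3 | 4 | 112 − 33 = 79 |

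**What share of a cohort?**

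The protocol gives no rate for such increases. Assuming 1, 2 or 3 subjects in a cohort of 8: 1/8 = 12.5%, 2/8 = 25%, 3/8 = 37.5%. Section 12.3 analyses missing data on reduced denominators unless the SAP specifies otherwise, so later-visit summaries would shrink by those shares. These are upper figures: they require every affected subject to be handled under Section 10 and the increase to precede the visit summarised.

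**The case against.** The strongest reply is that the rules can be read together. Section 8.4.3 does not say the subject stays in the study, and the follow-up sentence in 8.3 and 5.1 cannot be absolute, because Section 8.1 lists eight grounds for ending participation early. Section 10 would then be one more ground. This does not hold: Section 8.4.3 addresses this exact trigger with a different consequence and with discretion, and Section 8.1 does not list the trigger.

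The clarification letter did tell sites to read the sentence with Section 8.4.3. That shows intent and makes divergent handling less likely. But the letter kept the wording about leaving the study, and the later version omits the pointer.

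Several limits stand:

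- Ending participation after rescue, once dosing is complete, is a permissible choice rather than a contradiction, although it sits badly with the purpose of the Day 84 and Day 112 visits.
- The 1 to 3 subjects are an assumption, and no divergent handling has been shown.
- Much is kept either way: earlier data, membership of the analysis population, an Early Termination visit with IgG, PDAI and anti-desmoglein, follow-up of related adverse events, and recording of known later related events.
- The study is descriptive, with no formal sample size.

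**Conclusion.** The concern holds. During dosing, the protocol attaches two incompatible consequences to the same event, and nothing in the latest text resolves them. Per affected subject, the difference is 6 to 8 PDAI, 4 or 5 anti-desmoglein and 8 to 12 immunoglobulin time points for an increase just after Day 7, 14 or 21, against one Early Termination set. The cohort share of 12.5% to 37.5% rests on the assumed 1 to 3 subjects and on all of them leaving under Section 10.

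This cannot be left to the SAP, which cannot recover visits that were never held. It should be fixed. One caveat: the file is marked part 2 of 4, so a later amendment could already have changed the sentence.

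**What to change.** In Section 10 and in the synopsis row on prohibited concomitant treatments, replace the sentence with wording such as: *Subjects who require a significant increase in anti-pemphigus medication will be handled per Section 8.4.3 (no further study drug, if any remains) and will continue through all scheduled visits to Day 112, including when the increase occurs after the last dose.* The final clause goes beyond removing the contradiction; it also protects the Day 84 and Day 112 follow-up after dosing is complete.

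The date of the increase should be identifiable so that later values can be marked as post-rescue. Section 10 already requires dates and doses of concomitant medication, so a separate data field is probably unnecessary. How post-rescue values are analysed is for the SAP.

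The cost is one sentence reworded in two places, with no visits beyond those already scheduled.

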## 11 SAFETY

### 11.1 Safety Parameters

Clinical and laboratory AEs will be graded using the NCI CTCAE; Version 4.03 (See [Appendix A](#)).

Subjects will be monitored throughout the treatment and follow-up period for occurrence of AEs (acute, delayed, and/or cumulative), as well as for changes in clinical status, vital sign measurements, and laboratory data (including PD). Safety parameters to be measured/assessed include PEs, vital sign measurements, hematology, serum chemistries, urinalysis, and ECG.

### 11.2 Adverse Event Definition

An AE is defined as any untoward medical occurrence in a clinical trial subject associated with the use of a drug, whether considered drug related. An AE can be an unfavorable and unintended sign (e.g., an abnormal laboratory value finding), a symptom, or a disease temporally associated with the use of a drug, without judgment as to causality. An AE can arise from use of the drug (e.g., use in combination with another drug) and from any route of administration, formulation or dose, including an overdose. An AE also includes, but is not limited to, any clinically significant worsening of a pre-existing condition. Examples include:

- Any sign, symptom, physical finding, or laboratory result that has worsened in nature, severity or frequency compared to baseline;
- Reactions from an investigational drug, including those occurring because of an overdose, abuse of the study drug, withdrawal phenomena, sensitivity or toxicity;
- Concurrent illness that was not present or worsens in nature, severity, or frequency compared to baseline;
- Injury or accident; and/or
- Exacerbation of a pre-existing condition.

For data collection, all untoward events that occur after informed consent through the last study visit are to be recorded on eCRFs by the investigational site.

While pregnancy alone is not considered as an AE or SAE, any pregnancy complication(s) should be recorded as an AE(s) or SAE(s) (if applicable). Elective abortions without complications should not be regarded as AEs, unless they were therapeutic abortions (see below). Hospitalization for normal delivery of a healthy newborn should not be considered an SAE. If a female subject becomes pregnant during the conduct of the study, the Investigator must notify the Sponsor according to the procedures provided in [Section 11.3.8](#)).

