## PROCEDURES IN CASE OF EMERGENCY

### Serious Adverse Events

Any death or serious adverse event (SAE)\* occurring in a subject while receiving study drug or within 7 days of receiving study drug, even though the event may not appear to be study drug related, must be promptly reported (within 24 hours) by telephone or electronic communication to the sponsor (or designee).

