
Safety assessments
	
Safety assessments include AEs, serious adverse events (SAEs), PEs, vital sign measurements, clinical safety laboratory evaluations, ECGs, and reasons for treatment discontinuations due to toxicity. Safety assessments will be performed at specified time points and prior to discharge from the clinic. Vital sign measurements, including blood pressure, pulse rate, respiratory rate, and temperature will be monitored throughout the study. Pulse oximetry will be monitored during the study drug infusion and for 2 hours following the end of the infusion.

	
The National Cancer Institute Common Terminology Criteria for Adverse Events (NCI CTCAE; Version 4.03) will be used for grading clinical and laboratory AEs.
 
The AE reporting period for a subject enrolled in the study begins when the subject provides informed consent and is continued through the last study visit. All AEs that occur in the enrolled subjects during the AE reporting period must be recorded, regardless of the relationship of the AE to study drug. Any known untoward event that occurs beyond the AE reporting period that the Investigator assesses as related to study drug should also be recorded.

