### 6.10 Adverse Event Assessments

Information regarding the occurrence of AEs will be collected from the time the subject signs the informed consent form and continuing through the last study visit. Findings at screening and Day 0 (pre-dose) will be recorded as medical history. Any known untoward event that occurs beyond the AE reporting period that the Investigator assesses as related to study drug also should be reported as an AE.

Clinical AEs will be graded using the NCI CTCAE, Version 4.03 ([Appendix A](#)).

**Note:** AEs resulting in a subject's permanent discontinuation from the study, regardless of seriousness or relationship to study drug, MUST be promptly reported to the sponsor. Additionally, subjects must be followed until return to normal and/or resolution of the AE.

See [Section 11](#) for more information.

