## 8 REMOVING SUBJECTS FROM STUDY

Every reasonable effort will be made to keep the subject in the study; however, if a subject is withdrawn from the study, every effort will be made by the Investigator to complete and report the reasons for withdrawal as thoroughly as possible. The reason(s) for termination must be clearly documented on the appropriate page of the eCRF. Once a subject discontinues from the study for any reason, every effort will be made to collect all clinical and laboratory data as scheduled for the Early Termination Visit (See [Table 1](#)). A termination eCRF must be completed for all enrolled subjects.

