### 9.6.2 Potential Immune Effects

An antibody blocking FcRn is anticipated to have several effects. These include acceleration of catabolism of IgG, but not other immunoglobulin isotypes such as IgA and IgM, leading to dose-dependent decreases in circulating IgG levels by up to an estimated 50% from the baseline levels after a single dose and further decreases after multiple doses up to a 70% to 80% reduction. Based on studies in humans, it is expected that with a single dose, the nadir of this effect will occur approximately 5 days after dosing. The time course of recovery of IgG following dosing in the Phase 1a study suggests that a return to within 30% of baseline levels observed at pretreatment occurs within 4 weeks after a single dose and within 4 weeks after multiple doses as shown in NHPs.

Given the normal adult range of IgG of 500 to 1600 mg/dL ([Agarwal and Cunningham-Rundles, 2007](#); [Furst, 2009](#); [Gonzalez-Quintela et al., 2008](#); [Jolliff et al., 1982](#); [Keystone et al., 2007](#); [McMillan et al., 1997](#); [van Vollenhoven et al., 2013](#)), with a mean of 1150 mg/dL, a 50% decrease in the mean would be to 575 mg/dL and a 50% decrease from the low end of the normal range used for the inclusion criteria of 600 mg/dL would be to 300 mg/dL. An 80% decrease from baseline after multiple doses would result in IgG levels of 230 mg/dL and 120 mg/dL, respectively. While these levels are in the range found in patients with primary humoral immunodeficiency ([Ameratunga et al., 2013](#)), the levels will be transient. Further, as reported for other therapies used for pemphigus, the temporary (ie, less than 4 months) depletion of IgG (up to 95% reduction of total IgG as seen with immunoadsorption) does not appear to impart an increased risk of infection ([Eming and Hertl, 2006](#); [Furst, 2009](#); [Keystone et al., 2007](#); [Schmaldienst et al., 2001](#); [van Vollenhoven et al., 2013](#)). Study subjects will be monitored clinically for any infection. Further, commercial IVIG can be given to reverse the low IgG levels in case of a bacterial infection occurring while their IgG levels are decreased.

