**11.3.9.2 Time Frame for Reporting**

Any death, SAE or pregnancy experienced by the subject after informed consent through the last study visit, regardless of relationship to study drug, , must be promptly reported (within 24 hours of the Investigator becoming aware of the event) by telephone or electronic transmission to the sponsor (or designee).

Contact information for **SAE** reporting:

Medpace Clinical Safety  
Medpace SAE hotline:  
Telephone: PPD [redacted] dial P or PPD [redacted] dial P  
Facsimile: PPD [redacted] or PPD [redacted] D  
e-mail: PPD [redacted]

Additionally, the Investigator will be able to contact the **Medical Monitor**:

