### 11.3.9.3 Information to be Provided by the Investigator

SAEs must be recorded on the SAE form in the EDC system. This requirement includes all SAEs that occur after informed consent through the last study visit.

The minimum information required for SAE reporting includes identity of Investigator, site number, subject number, an event description, SAE term(s), onset date, the reason why the event is serious (i.e., the seriousness criteria) and the Investigator's assessment of the relationship of the event to study treatment. Additional SAE information including medications or other therapeutic measures used to treat the event, action taken with the study treatment due to the event, and the outcome/resolution of the event will be recorded. Paper forms for reporting SAEs will be provided to the study sites as back-up in case the EDC system is not accessible.

In all cases, the Investigator should continue to monitor the clinical situation and report all material facts relating to the progression or outcome of the SAE. Furthermore, the Investigator may be required to provide supplementary information as requested by Syntimmune or designee.

When reporting an SAE, the following additional points should be noted:

- When the diagnosis of an SAE is known or suspected, the Investigator should report the diagnosis or syndrome as the primary SAE term, rather than as signs or symptoms. Signs and symptoms may then be described in the event description. For example, dyspnea should not be used as an SAE term if the diagnosis, which caused the dyspnea, is known to be malignant pleural effusion.
- Death should not be reported as an SAE, but as an outcome of a specific SAE, unless the event preceding the death is unknown. In the exceptional case where the events leading to death are unknown, then death may be used as an event term. If an autopsy was performed, the autopsy report should be provided.
- While most hospitalizations necessitate reporting of an SAE, some hospitalizations do not require SAE reporting, as follows:
  - Elective or previously scheduled surgery, e.g., a previously scheduled ventral hernia repair
  - Procedures for pre-existing conditions that have not worsened after initiation of treatment
  - Pre-specified study hospitalizations for observation

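### A subject who leaves the study can drop out of routine AE collection within days of a dose, and the protocol's death and SAE reporting windows disagree

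*Protocol*

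**What the plan says.** **Routine AE window.** Section 11.2 says that "all untoward events that occur after informed consent through the last study visit are to be recorded on eCRFs". The synopsis (Safety assessments) says the AE reporting period "begins when the subject provides informed consent and is continued through the last study visit". Section 6.10 and the AE row of Table 1 end at the same point.

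**Deaths and SAEs.** Section 11.3.9.2 covers "Any death, SAE or pregnancy experienced by the subject after informed consent through the last study visit, regardless of relationship to study drug". Section 11.3.9.3 says of recording on the SAE form: "This requirement includes all SAEs that occur after informed consent through the last study visit". Section 11.3.1 bounds deaths in the same way. The emergency page at the front of the same protocol version instead ties reporting to dosing: a death or SAE during treatment or "within 7 days of receiving study drug, even though the event may not appear to be study drug related, must be promptly reported".

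**Late events.** The synopsis and Section 6.10 still ask for this to be recorded: "Any known untoward event that occurs beyond the AE reporting period that the Investigator assesses as related to study drug".

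**Leaving the study.** When a subject discontinues for any reason, Section 8 says "every effort will be made to collect all clinical and laboratory data as scheduled for the Early Termination Visit". Section 7.18 and Table 1 place that visit together with Day 112 and give it no interval from the last dose. Sections 5.1 and 8.3, each just after text on withdrawn subjects and replacements, say that subjects who do not receive every dose stay in follow-up through all scheduled visits.

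**Expected drug effect.** Section 9.6.2 puts the IgG nadir at about 5 days after a single dose. Return to within 30% of baseline "occurs within 4 weeks after a single dose and within 4 weeks after multiple doses as shown in NHPs".

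**The concern.** Safety and tolerability is the primary objective. A window defined only by the last visit gives a long observation period to those who stay and whatever happens to remain to those who go. Section 8.1 lets a subject leave at any time, by choice or for an AE, a laboratory change, a prohibited medication or the Investigator's judgement. If the Early Termination visit is then the last study visit, routine questioning about AEs can stop while IgG is still falling or has not recovered.

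The subject nevertheless remains in the summaries. Section 12.3.1 defines the ITT population as everyone dosed at least once, and Section 12.1 uses the population size as the default denominator for percentages. A subject seen for one day after dosing counts the same as one seen for 84 days. Analysis cannot recover events that were never collected, so this cannot be left to the SAP.

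For deaths and SAEs the trouble is different: two rules in the same document give different end dates.

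**Working it through.** **Inputs.** Doses on Days 0, 7, 14, 21 and 28 (Section 9.3); last scheduled visit Day 112 ± 5 days (Section 7.18); single-dose nadir about 5 days, recovery within 4 weeks = 28 days (Section 9.6.2); emergency-page window 7 days; 8 subjects per cohort, at most one replaced (Section 8.3).

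**1. The plan's own figure.** Screening 14 + treatment period 56 + follow-up 56 = 126 days, or 18 weeks. This matches the synopsis.

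**2. Completers.** Time observed after the last dose = 112 − 28 = 84 days (about 79 to 89 with the ± 5-day visit window).

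**3. Early leavers.** Time observed = day of the Early Termination visit − day of the last dose. For a subject with one dose:

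| Early Termination visit | Days after dose | Short of nadir (5 − days) | Short of recovery (28 − days) |
|---|---|---|---|
| Day 0, after infusion | 0 | 5 | 28 |
| Day 1 | 1 | 4 | 27 |
| Day 2 | 2 | 3 | 26 |

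The nadir column is valid only after one dose, because the protocol gives no nadir time after repeated doses. The recovery comparison also applies to a subject who leaves after all five doses. A visit on Day 29 is 29 − 28 = 1 day after dosing, 27 days short of 4 weeks (a figure the protocol takes from primates for multiple dosing). Sections 5.1 and 8.3 do not reach that subject on any reading, because no dose was missed.

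**4. The two death and SAE windows.** For a completer, the emergency page runs to 28 + 7 = Day 35, while Sections 11.3.1, 11.3.9.2 and 11.3.9.3 run to Day 112, which is 112 − 35 = 77 days later. For a one-dose subject with an Early Termination visit on Day 1, the emergency page runs to Day 7 and the Section 11 rules stop at Day 1. Neither rule contains the other. The 7-day window passes the single-dose nadir by 7 − 5 = 2 days and ends 28 − 7 = 21 days before the recovery point.

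**5. Effect on a percentage.** One subject whose event is missed changes a cohort incidence by 1/8 = 12.5 percentage points, or 1/9 = 11.1 if a dosed subject was replaced and nine were dosed.

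**6. Who is followed after withdrawal.** Section 8 prescribes an Early Termination visit for a subject discontinued from the study for any reason. Read literally, Sections 5.1 and 8.3 keep any subject with missed doses in follow-up to Day 112. A withdrawn subject with missed doses falls under both, and nothing says which governs.

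**The case against.** Much of the gap is already covered, and several stronger readings fail.

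- **A reader might infer that deaths and SAEs have no minimum window after dosing.** They do: the emergency page gives 7 days regardless of causality, past the single-dose nadir. A site that obeyed both rules would report to the later date. What stands is that the protocol never says so, and that 7 days ends well before 4 weeks.
- **Subjects who only stop dosing are not affected.** They are followed through all scheduled visits. Sections 5.1 and 8.3 may well be meant to cover withdrawn subjects too. That leaves the text unclear rather than plainly deficient for those with missed doses.
- **A reader might infer that missed events never reach the Dose Escalation Committee.** Known later events judged related are still recorded, with no time limit, and the rules in Sections 8.4.1 and 8.4.2 count related events only. Section 6.10 requires AEs that cause discontinuation to be reported promptly and followed. Section 8.1 requires attempts to reach subjects lost to follow-up. These provisions pursue existing events, survival or outstanding data; they do not solicit new AEs after a completed Early Termination visit.
- **A reader might apply the 5-day nadir after every dose.** Section 9.6.2 states it for a single dose.
- **A reader might point to the 28-day wording in superseded protocol text.** Superseded text is no evidence of an error in the current version.
- **Section 12.3 allows reduced denominators where data are missing because of dropout.** That concerns missing data points. An AE that nobody asked about leaves no missing value to trigger it.

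The size is also conditional: the protocol gives no withdrawal or event rate.

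**Conclusion.** The point holds in a limited form. For subjects who leave the study, rather than only dosing, routine AE collection has no minimum time after the last dose and can end 0 to 2 days after an infusion, against 84 days for completers. The death and SAE windows conflict between the emergency page and Section 11, and follow-up of withdrawn subjects with missed doses is unclear.

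The events at risk are non-serious AEs, and deaths or SAEs more than 7 days after dosing, that are judged unrelated or never learned of. Because early leavers count fully in the denominator, incidence can be understated, by up to 12.5 percentage points per affected subject in a cohort of 8, and unequally if withdrawals differ between cohorts. This assumes that at least one subject leaves early, that the Early Termination visit is treated as the last study visit, and that such an event then occurs. No sample size or error rate is involved. It is a worthwhile, low-cost improvement to the primary safety data, not a flaw that invalidates the design.

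**What to change.** 1. In the synopsis and Sections 6.10, 11.2, 11.3.1, 11.3.9.2 and 11.3.9.3, end AE, SAE and death collection at *the last study visit or 28 days after the last dose of study drug, whichever is later*. Make the same change in the AE row of Table 1. The 28 days match the 4-week recovery time in Section 9.6.2. They run to Day 28 after one dose and to Day 28 + 28 = Day 56 after five; completers, already followed for 84 days, see no change.
2. Bring the emergency page into line with that window.
3. State how the follow-up sentence in Sections 5.1 and 8.3 and the Early Termination visit in Section 8 apply to a subject discontinued from the study.
4. For such subjects who have not refused contact, collect AEs, SAEs and vital status by telephone 28 days after the last dose.

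The cost is a few sentences in the next amendment, one call per early leaver and a slightly longer data-collection tail. No treatment changes. Subjects who refuse contact will still be missed, so their observation time should be visible in the report.
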